1.3 Study Objectives

The overall study objective is to assess the long-term safety and tolerability of simufilam.

This study has separate sets of objectives for the OL and RW phases. Safety and tolerability are the primary objectives of the OL phase. The primary objective of the RW phase is to assess patient response to blinded, randomized drug withdrawal.

Because drug safety in non-responders can be a critical component of a drug's risk-reward assessment, all patients who completed the 12-month OL phase were eligible to enter the RW phase, regardless of whether they previously showed an apparent response (or not) to open-label drug treatment.

Some study objectives overlap in the OL and RW phases. Hence, objectives are summarized separately below for the OL and RW phases, and for objectives spanning multiple phases. All objectives apply to mild-to-moderate Alzheimer's Disease (AD) patients, 50-85 years of age.

Objectives for the Open-label (OL) phase

- Assess the long-term safety and tolerability of OL treatment with simufilam 100 mg b.i.d. during 12-month repeat-dose oral administration.
- Assess mean changes from baseline on MMSE and compare those changes between patients with mild vs moderate AD.

Objectives for the Randomized Withdrawal (RW) phase

- Assess the safety and tolerability of treatment with simufilam 100 mg b.i.d. versus matching placebo over the 6-months study period.
- Assess patient response to blinded, randomized drug withdrawal on ADAS-Cog11.

Objectives Spanning Overall Study

Exploratory objectives tested across multiple phases are to:

- Characterize the safety and tolerability of simufilam during and up to 24 months of treatment.
- Assess mean changes from baseline on biomarkers and compare those changes between patients with mild vs moderate. For CSF biomarkers, change from baseline to M6 or M12 will be calculated. Plasma biomarkers will be analyzed for change from baseline to M6 and M12 for the OL phase and from M12 to M18 for the RW phase.

Note: All biomarker assessments in this study are exploratory endpoints that are not patient safety related, are 'Research Use Only' products, and, hence, are not intended to be compliant with FDA's Quality System Regulation (QSR) or ISO equivalent.

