2.2 Study Design

All patients received simufilam 100 mg b.i.d. as coated oral tablets.

The first 12 months is an open-label treatment of simufilam 100 mg b.i.d. Month 12 to Month 18 is a RW phase in which patients who completed OL treatment are randomized (1:1) to simufilam 100 mg b.i.d. or matching placebo. Month 18 to Month 24 will be an additional 6 months of open-label simufilam 100 mg b.i.d.

Simufilam and placebo will be administered as coated oral tablets. Patients who were enrolled prior to the protocol amendment could continue upon reconsenting to the RW and final 6-month open-label portion.

All patients provided consent to enroll into this study. Patients reported to the clinic in the morning of Day 1. Prior to dosing, patients completed the following baseline measures: ADAS-Cog11, C-SSRS, ECG, vital signs, clinical labs, urinalysis, listen to heart and lungs, and MMSE. A blood sample was collected for plasma-based biomarkers.

Patients returned to the clinic every month through Month 3 and every 1.5 months through Month 12. Visits on Months 4.5, 7.5 and 10.5 included vital signs, listening to heart and lungs, AE monitoring, C-SSRS and drug dispensation and accountability only. Visits at Months 4.5, 7.5 and 10.5 could be performed by telemedicine, based on the judgement of the Investigator. Only AE-monitoring and C-SSRS assessment could be performed remotely. After Month 12, visits occurred on Months 13, 15, 18, 21 and 24. Patients completing Month 12, and who chose to continue into the RW phase of the study, prior to availability of drug supply for the RW phase continued with active treatment until drug supply was ready and therefore had an additional "Withdrawal Day 1" visit before resuming with the Month 13 visit one month later. Collection of saliva for genetic testing occurred at Month 15.

Blood draws for clinical laboratory testing and urine collection for urinalysis were performed at Day 1 and Months 1, 2, 3, 6, 9, 12, 15, 18, 21 and 24. Safety assessments of vital signs and listening to heart and lungs were conducted at Months 2, 4.5, 7.5 and 10.5 visits.

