Study data identified in the schedule of events are collected, and source verified, on the electronic data capture tool: Axiom Fusion eClinical Suite (Axiom, Toronto, ON, Canada).

All study data will be formulated into regulatory compliant data sets to provide transparency, traceability, and integrity of trial analysis results from the collection source. Observed study data will be mapped to the CDISC Study Data Tabulation Model (SDTM) and serve as the source data from the trial. All study analyses will be completed using analysis data sets that are derived from the SDTM and follow the CDISC Analysis Data Model (ADaM) architecture. All planned analyses will be performed using the ADaM data sets developed for this study.

The following Implementation Guides will be referenced for the configuration of SDTM and ADaM datasets:

- SDTM Model 1.7 and SDTM Implementation Guide (SDTM IG) version 3.3 will be used.
- ADaM Model 2.1 and ADaM Implementation Guide (ADaM IG) version 1.3 will be used.

Statistical Summaries

All statistical tests in all phases of the study will be two-sided and p-values of less than or equal to 0.05 will be considered statistically significant.

All p-values will be rounded and displayed in 3 decimal places. If a p-value less than 0.001 occurs, it will be shown in tables as <0.001.

Descriptive summaries of variables will be provided where appropriate. For continuous variables, the number of non-missing values (n) and the median, mean, standard deviation, minimum, and maximum will be tabulated by treatment. For categorical variables, the counts and proportions of each value will be tabulated by treatment.

Data will be presented as listings where applicable. Data not patient to analysis according to this plan will not appear in any tables or graphs but will be included in the data listings.

4 Analyses Spanning Overall Study

For the below analyses, it will be summarized by overall.

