4.6 Treatment Compliance and Extent of Exposure

Study medication compliance will be calculated based on the numbers of tablets dispensed minus the number of tablets returned divided by the expected number of tablets based on the duration of the patient's participation in the study and will be summarized as continuous and categorical variables. Compliance will be summarized as a continuous outcome using mean, SD, median, min, and max. For the categorical analysis, a patient will be considered compliant if the amount of medication taken is within the range of 75% - 125% of the amount of medication planned to be taken.

Total number of days the patient is on study drug will be summarized as a continuous variable. The Days a patient is on study drug will be calculated as the number of days from date of first dose to date of last dose plus 1.

Treatment compliance will be summarized overall.

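### SAP 4.6 defines one overall first-to-last-dose day count and no simufilam-only exposure, so withdrawal-phase placebo days are pooled with simufilam days

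*SAP*

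**What the plan says.** SAP 4.6 (Treatment Compliance and Extent of Exposure) plans one duration variable: "Total number of days the patient is on study drug will be summarized as a continuous variable". It is "calculated as the number of days from date of first dose to date of last dose plus 1". The formula has no term for treatment or study period.

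The level of summary is set in the lead-in to SAP Section 4: "For the below analyses, it will be summarized by overall". SAP 4.6 repeats this for compliance: "Treatment compliance will be summarized overall".

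SAP 2.2 describes three consecutive periods. For the first, "The first 12 months is an open-label treatment of simufilam 100 mg b.i.d". From Month 12 to Month 18, patients who completed it are "randomized (1:1) to simufilam 100 mg b.i.d. or matching placebo". Month 18 to Month 24 is open-label simufilam again. The same section opens with an unqualified sentence: "All patients received simufilam 100 mg b.i.d. as coated oral tablets".

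Among the objectives that span the study, SAP 1.3 lists: "Characterize the safety and tolerability of simufilam during and up to 24 months of treatment".

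**The concern.** The safety objective is about simufilam, and time on simufilam is its basic descriptor. For a placebo-arm patient who returns to open-label drug, the placebo interval lies in the middle of the first-to-last-dose span and is counted in full. No other measure in the SAP recovers simufilam time, so the only figure under the heading of exposure mixes the two treatments.

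The SAP treats the arms as different exposures elsewhere. SAP 1.3 and 7.1 compare continuous with interrupted dosing, and SAP 3.2 analyzes safety as treated. The 4.6 day count does not carry that distinction. At stake is how the clinical study report describes the length of simufilam treatment behind its safety data.

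**Working it through.** The documents state no exposure total, so there is no plan figure to reproduce. The check applies the SAP 4.6 formula to the design, then removes placebo time. One month is 365.25/12 = 30.4375 days.

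**Inputs**
- Formula: last dose date - first dose date + 1 (SAP 4.6).
- Periods: 12 months simufilam, 6 months randomized 1:1, 6 months simufilam (SAP 2.2).
- Numbers: 220 enrolled, 43 dropped out in the open-label phase, 21 did not continue (SAP 2.5).
- Visit window: plus or minus 5 days (Protocol 7.2.3).

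**One placebo-arm patient who completes Month 24**
- SAP 4.6 count: 24 × 30.4375 + 1 = 731.5 days.
- Placebo interval: 6 × 30.4375 = 182.6 days, or about 173 to 193 if the visit at each end moves by 5 days.
- Simufilam days: 731.5 - 182.6 = 548.9.
- Overstatement: 182.6/548.9 = 33%. Placebo is 25% of the reported days.

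If the last dose is at Month 18 instead, the count is about 548 days against about 365 on simufilam: 6/12 = +50%.

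**Cohort**
- Could enter the withdrawal phase: 220 - 43 - 21 = 156. The SAP does not state the number randomized or the number per arm; 1:1 gives about 78 per arm.
- Placebo time if all 78 complete the phase: 78 × 0.5 = 39 patient-years.

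The size of the overall overstatement depends on retention, which must be assumed. In every row the 21 contribute 1 year each.

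| Assumption | Total (patient-years) | Placebo | Simufilam | Overstatement |
|---|---|---|---|---|
| All 156 finish Month 24; the 43 average 0 months | 156×2 + 21 + 0 = 333 | 39 | 294 | 13.3% |
| Same; the 43 average 6 months | 312 + 21 + 21.5 = 354.5 | 39 | 315.5 | 12.4% |
| Same; the 43 average 12 months | 312 + 21 + 43 = 376 | 39 | 337 | 11.6% |
| All placebo patients stop 3 months into the phase, simufilam arm finishes Month 24; the 43 average 6 months | 78×2 + 78×1.25 + 21 + 21.5 = 296 | 19.5 | 276.5 | 7.1% |
| All 156 stop at Month 18; the 43 average 6 months | 156×1.5 + 21 + 21.5 = 276.5 | 39 | 237.5 | 16.4% |

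Extra open-label time before Withdrawal Day 1 (Protocol 7.2.8 and 7.2.9) is true simufilam time. The documents give no durations for it, so it is left out. Including it would raise total and simufilam time equally and slightly lower the percentages; the placebo days would not change.

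**The case against.** The strongest reply is that the formula does what its label says. SAP 4.6 counts days on study drug, and Protocol section 6 (6.1 and 6.2) covers both simufilam and placebo under that term, so placebo days are study-drug days. This stands: the count is not a miscalculation. However, SAP 2.4, headed as study drug dosing, names only simufilam, and no second measure is provided. The one figure available for the simufilam objective is therefore the pooled one.

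Several stronger readings are tempting, and the documents do not support them.

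- A reader might infer that patients will be miscounted as treated with simufilam for 24 months. SAP 4.6 plans only a continuous summary, with no 12-, 18- or 24-month categories; counts by period come from the disposition table in SAP 4.1. The mean, median and maximum would still include placebo-arm completers at about 24 months.
- A reader might infer that the annualized adverse event rates are diluted. They are not: SAP 4.7 defines its own time at risk, ending at Month 12 or early termination. Adverse events are also summarized separately for the open-label and withdrawal phases.
- A reader might take six months as the excess for every placebo-arm patient. It applies only to those who complete the withdrawal phase, and SAP 6.1 itself expects discontinuations for lack of efficacy.
- A reader might call the opening sentence of SAP 2.2 false. It is true of the open-label phase, and the next paragraph states the randomization to placebo. It needs qualifying, not retracting.

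SAP 3.2 also has a general rule to tabulate by treatment. It does not settle the matter: the Section 4 lead-in says overall, and a by-arm table using the same formula would show about 731 days for completers in both arms.

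**Conclusion.** The point holds as a gap in the exposure definition. Following SAP 4.6 as written gives a pooled count that is correct for any study tablet and too large for simufilam.

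The 33% excess for a placebo-arm patient who completes Month 24 follows from the design alone. The cohort figures are conditional. The 39 patient-years is close to a ceiling, because it needs all of about 78 derived placebo patients to complete the withdrawal phase. The 12-13% needs all 156 to finish Month 24, and the roughly 7-16% shows how far other retention assumptions move it.

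No efficacy inference and no other specified analysis uses this day count. The consequence is confined to a descriptive summary, but that summary is the main descriptor of exposure for the stated long-term safety objective, so it should be corrected.

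**What to change.** In SAP 4.6, calculate simufilam exposure by period and actual treatment, as the sum of:
- open-label days from Day 1 to Month 12, including any extension before Withdrawal Day 1;
- withdrawal-phase days for the simufilam arm only;
- open-label days from Month 18 to Month 24.

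Report placebo days as a separate variable, and show the summary by continuous versus interrupted arm as well as overall. If the first-to-last-dose count is kept, label it as days on simufilam or placebo. In SAP 2.2, qualify the sentence that all patients received simufilam so that it refers to the open-label phases.

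The cost is a wording change and a small amount of programming. It needs period-level dose dates and the treatment received; SAP 4.6 mentions only overall first and last dose dates, so their availability should be confirmed. The reported simufilam exposure will be smaller.

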4.7 Safety Analysis

Adverse Events

Treatment emergent AEs (TEAEs), defined as AEs that first occurred or worsened after first dose, will be summarized overall. Summary of TEAEs occuring in the Open-label phase (D1-M12 and M18-M24) will be summarized in one group . TEAEs occurring in Double-blind (RW) phase (M12-M18) will be summarized in other group. All the listings mentioned below to be provided for both the groups. The incidence of TEAEs will be reported as the number (percent) of patients with TEAEs within System Organ Class (SOC) and Preferred Term (PT). Patients will be counted only once within a SOC and PT, even if the patient experienced more than one TEAE within a specific SOC and PT. The number (percent) of patients with TEAEs will also be summarized by maximum severity and relationship. The denominators for calculating the percentages for summaries will be based on the number of patients in the analysis population enrolled to each group.

The following types of summary will be provided for Incidence of TEAEs:

- Treatment Emergent Adverse Events by System Organ Class and Preferred Term;
- Treatment Emergent Adverse Events by System Organ Class, Preferred Term and Maximum Severity;
- Treatment Emergent Adverse Events by System Organ Class, Preferred Term and Relationship to Study Drug;

The annualized incidence rate of AEs per person-years at risk, calculated as (365.25*number of AE occurrences)/(total treatment period with patients at risk of AE), will also be reported by most prevalent PT in the SOC.

The total period at risk for each patient will be defined as the period from first dose of study treatment to the date of the End of Treatment (EOT) (Month 12) or Early Termination (ET) visit for prematurely treatment discontinued patients. Annualized incidence rates will be expressed in terms of events per 100 patient years exposure.

Vital Signs

For Months 6, 12, 18, and 24, summary statistics will be provided (study population size, mean, SD, minimum, median, and maximum) for each vital sign parameter, by treatment group and overall. Summary statistics for change from baseline values will also be presented. Numbers and percentages of patients with abnormal values will be included.

ECG

The 12-lead ECG tests will be summarized by treatment group and overall using qualitative statistics per each scheduled visit. The summary will include the number and percentage of patients with test values classified as normal, abnormal (clinically significant), abnormal (not clinically significant) and unevaluable.

Laboratory Data

For months 6. 12, 18, and 24, summary statistics will be provided (study population size, mean, SD, minimum, median, and maximum) for each laboratory test and their change from baseline by treatment group and overall, along with their change from baseline screening values will be presented overall, for each scheduled visit. Numbers and percentages of patients with abnormal values will be included.

Physical Examination

Full physical examination data will be listed overall, by enrollment group and patient only.

5 Analysis of Open-Label Phase

The following efficacy analyses will be applied to data from the OL phase (D1-M12).

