4. SUMMARY OF STUDY DESIGN

The first 12 months is an open-label treatment of simufilam 100 mg b.i.d. for patients who completed prior Phase 2 studies PTI-125-02 and PTI-125-03. New patients are included so that up to 200 patients are enrolled in this study. Month 12 to Month 18 is a randomized withdrawal phase; patients will be randomized to continue taking simufilam 100 mg b.i.d. or matching placebo. Month 18 to Month 24 will be an additional 6 months of open-label simufilam 100 mg b.i.d. Simufilam and placebo will be administered as coated oral tablets. Patients who were enrolled prior to this amendment can continue upon reconsenting to the randomized withdrawal and final 6-month open-label portion.

All patients will provide consent to enroll into this study. Unless patients have a prior positive amyloid PET scan, MRI showing hippocampal volume loss or other prior evidence of AD, patients will undergo a CSF draw (if all other screening criteria are met) to confirm a total tau/A β_{42} ratio ≥ 0.28 .

Patients will report to the clinic in the morning of Day 1. Prior to dosing, patients will complete the following baseline measures: ECG, vital signs, clinical labs, urinalysis, listen to heart and lungs, ADAS-Cog11, neuropsychiatric inventory (NPI), geriatric depression scale (GDS), and the C-SSRS. A blood sample will be collected for plasma-based biomarkers and genetic testing.

Patients will return to the clinic every month through Month 3 and every 1.5 months through Month 12. Visits on Months 4.5, 7.5 and 10.5 will include vital signs, listening to heart and lungs, AE monitoring, C-SSRS, and drug dispensation and accountability only and may be conducted by telemedicine, based on the judgement of the Investigator. After Month 12, visits will be on Months 13, 15, 18, 21 and 24. Patients completing Month 12 prior to availability of drug supply for the randomized withdrawal phase will continue with active treatment until drug supply is ready and therefore will have an additional "Withdrawal Day 1" visit before resuming with the Month 13 visit one month later.

PK blood samples will be obtained in the morning before dosing at return visits on Months 15 and 18.

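### SAP 4.7 pools adverse events from two non-adjacent open-label periods, so crude percentages span up to 18 versus 6 months and events on restarting simufilam are diluted or masked in the summary tables

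*SAP*

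**What the plan says.** SAP 4.7 (Adverse Events) plans an overall summary of treatment-emergent adverse events (TEAEs) and two phase groups. For the first: "Summary of TEAEs occuring in the Open-label phase (D1-M12 and M18-M24) will be summarized in one group". For the second: "TEAEs occurring in Double-blind (RW) phase (M12-M18) will be summarized in other group". The counting rule is "Patients will be counted only once within a SOC and PT, even if the patient experienced more than one TEAE". Percentages are taken over the patients in the analysis population who were enrolled to the group.

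The section adds an annualized rate per 100 patient-years. A patient's period at risk runs from first dose to the end-of-treatment visit, identified as Month 12, or to the early termination visit.

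The adverse event text describes no split of the open-label group by period, none by prior RW arm, and none of the RW group by randomized arm. SAP 1.3 nevertheless sets safety objectives for simufilam versus placebo in the RW phase and for treatment lasting up to 24 months.

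On visits, SAP 2.2 says "Patients returned to the clinic every month through Month 3 and every 1.5 months through Month 12" and then "After Month 12, visits occurred on Months 13, 15, 18, 21 and 24". Protocol section 4 gives the same schedule and includes adverse event monitoring at the interim visits: "Visits on Months 4.5, 7.5 and 10.5 will include vital signs, listening to heart and lungs, AE monitoring, C-SSRS".

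**The concern.** The pooled group joins two periods with different populations and drug histories. Day 1-Month 12 is a first year of treatment in everyone enrolled. Months 18-24 include only patients who went through the RW phase, about half of whom restart simufilam after six months on placebo.

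Two things follow. First, a crude percentage depends on how long patients are watched, so the open-label column will exceed the RW column even if the underlying risk never changes. Second, a patient who had a given term in year 1 adds nothing to the pooled count if it returns on restart, and a term new on restart is divided by a denominator that includes the whole first-year population.

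At stake is whether the main adverse event tables can show what happens on re-exposure after a randomized interruption, and whether their columns can be read side by side. An exposure-adjusted rate is the usual remedy for the first problem, so the definition of the period at risk matters.

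**Working it through.** The documents give no adverse event rates, so there is no planned figure to reproduce. Event rates and dropout timing below are assumptions.

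**Inputs**
- Enrolled 220; dropped out in the first open-label period 43; did not reconsent 21 (SAP 2.5). I assume all 220 were dosed.
- RW allocation 1:1 (SAP 2.2).
- Nominal lengths: 12, 6 and 6 months.

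**1. Patients reaching the later periods**
- Entering RW, at most: 220 − 43 − 21 = 156.
- Restarting after placebo, if nobody leaves during RW: 156 / 2 = 78.

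Both figures are derived, not stated in the documents.

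**2. Crude percentage at a constant hazard**

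With 6-month incidence p, incidence is 1 − (1 − p)² over 12 months and 1 − (1 − p)³ over 18. Assume the 43 leave at Month 6, the 21 stop at Month 12 and nobody leaves later. The pooled column then shows

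[156 × (1 − (1 − p)³) + 21 × (1 − (1 − p)²) + 43 × p] / 220.

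- p = 10%: (156 × 0.271 + 21 × 0.19 + 43 × 0.10) / 220 = (42.3 + 4.0 + 4.3) / 220 = 23.0%, against 10% in the RW column.
- p = 30%: (156 × 0.657 + 21 × 0.51 + 43 × 0.30) / 220 = (102.5 + 10.7 + 12.9) / 220 = 57.3%, against 30%.

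For less common terms (12-month incidence 2% to 20%), the same attrition gives a ratio of 2.49 to 2.29.

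**3. Dilution of events on restart**

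If a fraction r of the 78 restarting patients has a given event, the most it adds to the pooled column is 78 × r / 220.

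| r (assumed) | Patients | Own denominator (78) | Largest addition to pooled column (220) |
|---|---|---|---|
| 5% | 3.9 | 5% | 1.8 points |
| 10% | 7.8 | 10% | 3.5 points |
| 20% | 15.6 | 20% | 7.1 points |

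Each affected patient who already had the term in year 1 adds nothing.

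**4. The annualized rate**
- First-period person-time, with the 43 leaving at Month 6: 177 × 1 + 43 × 0.5 = 198.5 patient-years (177 = 156 + 21).
- Months 18-24, with no later dropout: 156 × 0.5 = 78 patient-years.
- If Month 18-24 events enter the numerator but person-time stops at Month 12, the open-label rate is overstated by (198.5 + 78) / 198.5 = 1.39 at a constant event rate. The factor runs from 1.36 if all 43 leave at Month 12 (298 / 220) to 1.44 if they leave at once (255 / 177).
- If only events to Month 12 are counted, the rate is sound for year 1, but RW and Months 18-24 have none.

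**5. Contact density**
- Day 1-Month 12: visits at Months 1, 2, 3, 4.5, 6, 7.5, 9, 10.5 and 12, so 9 / 12 = 0.75 per month.
- RW: Months 13, 15 and 18, so 3 / 6 = 0.50.
- Months 18-24: Months 21 and 24, so 2 / 6 = 0.33.
- The two groups as reported: 11 / 18 = 0.61 against 0.50.

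With complete recall this creates no difference. Suppose instead that capture over a gap of g months is (1 − exp(−λg)) / (λg), with λ assumed between 0.05 and 0.3 per month. Capture in Months 18-24 is then 0.96 to 0.80 of year 1, but capture in RW is 0.99 to 0.945 of the pooled open-label group.

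**The case against.** The strongest reply is that this is a descriptive safety section. It plans no test and no stated contrast between the open-label and RW columns. The RW safety objective compares arms over the same six months, where durations match. That is fair, and it limits the harm to interpretation. But side-by-side percentages invite comparison, and the adverse event text does not describe the arm split which that objective needs. SAP 3.2 says categorical data are tabulated by treatment, while the opening of section 4 says overall, so the layout is ambiguous at best.

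A reader might infer that events on restart are hidden altogether. The documents do not support that. SAP 3.2 lists all eCRF data, and SAP 4.7 provides listings for both groups. Vital signs and laboratory data at Months 18 and 24, and ECG by visit, are also summarized by treatment group. If that means RW arm, they offer some view of restarting patients. The masking is in the adverse event summary tables.

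A reader might also infer that the thinner visit schedule produces period differences by construction. It does not. Protocol 9.1 has the investigator ask about the whole interval back to the previous assessment and record spontaneous reports too. The steepest contrast (0.75 against 0.33) also lies inside the pooled column. What remains is a possible minor ascertainment bias.

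A third tempting figure is 10% rising to 27%, or 30% to 66%. That requires all 220 patients to be followed for 18 months, which SAP 2.5 rules out.

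Finally, SAP 1.2 says versions 1.0 and 2.0 were used for the open-label and RW analyses. They may contain separate first-year tables, but that cannot be seen here. Version 3.0 governs the clinical study report.

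**Conclusion.** The point stands as a weakness of tabulation and of the rate definition. Followed as written, SAP 4.7 gives crude percentages over up to 18 versus 6 months, roughly a 1.9- to 2.5-fold difference at an unchanged hazard over the incidences tried. It also dilutes or masks events in about 78 restarting patients. The planned rate does not repair this, because its person-time stops at Month 12 or early termination; a mismatched numerator would inflate the open-label rate by about 1.4.

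These sizes rest on a constant hazard, all 220 enrolled being dosed, the 43 dropouts leaving at Month 6 (varied for the rate), and no dropout after Month 12. Later dropout would lower the 156, the 78 and the factor of 1.4. The restart event rates are illustrative. Contact density merits a footnote only. The section should be changed, since it feeds the main safety tables for the study's overall objective and the remedy is cheap.

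**What to change.** In SAP 4.7, replace the two phase groups with:
- Day 1-Month 12, stating where open-label time between Month 12 and Withdrawal Day 1 is assigned. Neither group now claims it, and the schedule lists no adverse event monitoring at that visit.
- RW, by randomized arm.
- Months 18-24, by prior RW arm (continuous versus restarting).

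Give each its own denominator (patients dosed in that period), count each patient once per term per period, and report period-specific person-time. Redefine the period at risk to match, so that the events counted and the time at risk cover the same interval. Compare periods only by exposure-adjusted rates. Footnote the scheduled contacts: 9 in 12 months, 3 in 6 and 2 in 6.

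The variables are already in use: SAP 4.1 reports disposition by period, and SAP 7.1 compares continuous with interrupted treatment. The cost is revised wording and programming, longer tables, and Month 18-24 subgroups of at most about 78 patients (39 patient-years) each, in which uncommon events will be imprecisely estimated. No new data are needed.

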3.2 General Considerations that Apply to All Phases

Analysis Populations

Three analysis sets are defined for each phase of the study.

- The Full Analysis Set (FAS) includes all patients who receive at least one dose of study treatment and have evaluable efficacy records at baseline and post-baseline visits.
- The Per Protocol Analysis Set (PP) is the same as the FAS minus patients with major violations of protocol inclusion or exclusion criteria, e.g., other or interfering neurologic disorders such as posterior cortical atrophy, frontotemporal dementia, multiple psychiatric diagnoses, taking anxiolytics, or significant history of cardiovascular disease. PP also excludes patients who refused assessments for one or more visits and patients who were < 65% compliant by pill counts.
- The Safety analysis set will include all patients who receive at least one dose of the study treatment. All safety analyses will be based on the Safety population. Patients will be analyzed as treated.

Defining Mild vs Moderate Baseline Severity

For the purposes of analyses in all phases of the study, mild AD is defined as baseline MMSE \geq 21, and moderate AD as baseline MMSE \leq 20.

Management of Analysis Data

All tables, listings and figures will be presented in landscape format. All outputs will be sent to CSI as electronic files in Rich Text Format (RTF) format documents.

Definition of Analysis Timepoints

Scheduled analysis visits are visits upon scheduled time points as specified in Table 1 Schedule of Time and Events.

Scheduled analysis visits during the study period will be windowed to the nearest scheduled visit within the same phase.

Unscheduled visits are visits with data not collected at scheduled time points. Unscheduled visits will be windowed to the nearest scheduled visit as described above.

For the purposes of calculating change from baseline in the tables, if there is an unscheduled visit with a value and the visit BEFORE the unscheduled visit (i.e., scheduled visit) does not have a value for that assessment, the value associated with unscheduled visit can be used. Else, disregard the unscheduled visit, if scheduled visit is available and has a value.

There will be one valid value of assessment kept for each scheduled analysis visit in summary / analysis statistics. All unscheduled visits will be included as collected in eCRF in listings.

Handling of Missing Data and Partial Dates

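### SAP 4.7 groups adverse events by phase and names no arms for the randomized withdrawal phase, so read literally its tables pool simufilam and placebo

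*SAP*

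**What the plan says.** SAP 1.3 lists among the RW objectives: "Assess the safety and tolerability of treatment with simufilam 100 mg b.i.d. versus matching placebo over the 6-months study period". SAP 2.2 randomizes patients who complete the open-label period 1:1 to simufilam or placebo for Months 12 to 18.

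SAP 4.7 asks for an overall TEAE summary and then for two groups. Day 1 to Month 12 and Months 18 to 24 are combined in one. For the other: "TEAEs occurring in Double-blind (RW) phase (M12-M18) will be summarized in other group". On outputs it adds: "All the listings mentioned below to be provided for both the groups". Percentages use denominators "based on the number of patients in the analysis population enrolled to each group". The three TEAE tables are by SOC and preferred term, by maximum severity, and by relationship; no arm is mentioned in any of them. The lead-in to section 4 reads: "For the below analyses, it will be summarized by overall".

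Elsewhere in 4.7, vital signs are summarized "for each vital sign parameter, by treatment group and overall", and ECG and laboratory data carry the same split.

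Two general statements in SAP 3.2 bear on the point. For categorical variables, "the counts and proportions of each value will be tabulated by treatment"; for the Safety set, "Patients will be analyzed as treated".

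**The concern.** The RW phase is the only part of this study with a concurrent randomized placebo arm, so it is the only place where adverse events on simufilam can be set against a control. The only groups the adverse-event paragraph defines are phases. A programmer who follows it as written produces one RW column that holds both arms.

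The clinical study report's RW adverse-event tables would then show neither the size nor the direction of any arm difference, and the adverse-event part of the RW safety objective would go unanswered. By-arm vital signs, ECG and laboratory data answer it only in part. SAP 1.2 makes version 3.0 the plan for the final data and the clinical study report, so its wording matters.

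Even with arm columns the comparison would be descriptive only: the arms are small, and RW entrants have already completed 12 months on drug.

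**Working it through.** The plan gives no figure to reproduce here. The check is a reading of the text, followed by an illustration of what a pooled column hides.

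**1. The passages side by side**

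| Place | What it gives for RW |
|---|---|
| SAP 1.3, RW objectives | Safety comparison of simufilam with placebo |
| SAP 4.7, TEAEs | RW is one group; denominators by group; no arm named |
| SAP 4.7, vital signs, ECG, laboratory | By treatment group and overall |
| SAP 4.7, annualized adverse-event rate | Period at risk ends at Month 12 or early termination |
| SAP 3.2, Statistical Summaries | General rule: tabulate by treatment |
| SAP 6 | RW efficacy only |
| Protocol 10.4 | For adverse events, MedDRA mapping only |

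The 4.7 TEAE text is the specific rule, and it groups by phase. The only text that points to arm columns for TEAEs is the general rule in 3.2. Neither SAP 6 nor Protocol 10.4 settles the matter. The annualized rate does not help either: for a patient who continues past Month 12, it defines no person-time in RW.

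**2. Patients in RW**

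Inputs from SAP 2.5: 220 enrolled, 43 dropped out in the open-label phase, 21 did not continue.

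- Maximum entering RW: 220 − 43 − 21 = 156, which is 156/220 = 70.9% of those enrolled.
- Per arm at 1:1: 156/2 = 78.

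The SAP states no RW number, so 156 is a derived ceiling.

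**3. What a pooled cell hides**

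Let k patients have a given event, a on simufilam and b on placebo, with a + b = k and k ≤ 78. The pooled percentage is k/156. The arm difference is (a − b)/78, which can lie anywhere from −k/78 to +k/78. Because k/78 = 2 × k/156, the possible difference runs to plus or minus twice the pooled percentage.

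The documents give no adverse-event rates, so the counts below are assumed:

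| k | Pooled | Possible arm difference |
|---|---|---|
| 5 | 5/156 = 3.2% | ±6.4 points |
| 10 | 10/156 = 6.4% | ±12.8 points |
| 24 | 24/156 = 15.4% | ±30.8 points |

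Three splits that all pool to 10/156 = 6.4%, with Newcombe 95% confidence intervals:

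| Simufilam vs placebo | Difference | 95% CI |
|---|---|---|
| 10/78 vs 0/78 | +12.8 points | 5.4 to 22.0 |
| 5/78 vs 5/78 | 0 | −8.5 to 8.5 |
| 0/78 vs 10/78 | −12.8 points | −22.0 to −5.4 |

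If only 60 per arm entered, 10/60 vs 0/60 would pool to 10/120 = 8.3%, with a difference of +16.7 points (7.2 to 28.0).

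**The case against.** The strongest reply is that 4.7 does not forbid arm columns and that 3.2 supplies them. The 3.2 considerations are declared to apply to all phases, and TEAE incidence is a categorical count. On that view the two groups are two sets of outputs, one open-label and one RW, each tabulated by treatment. That reading also fits the RW objective.

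The supporting evidence for pooling can be discounted too. The section 4 lead-in also governs vital signs, ECG and laboratory data, which are split by arm, so it cannot by itself mean that arm columns are absent. The SAP asks for vital signs and laboratory data by treatment group even at Months 6 and 12, when everyone has been on open-label drug, so its wording is loose throughout. Arm-level data would in any case survive in the listings and analysis data sets. The numerical illustration would hold for any pooled 1:1 table.

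Much of this stands. The lead-in is weak evidence, the consequence depends on the pooled reading being programmed, and the illustration says nothing about how likely that is. But the 3.2 rule is general and qualified as applying where appropriate, and analysing patients as treated assigns them to a treatment without fixing table columns. The grouping and denominator rule in 4.7 is more specific and is built on phase. Two programmers could produce different RW adverse-event tables from this text.

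**Conclusion.** The point holds as a defect in the version 3.0 wording. Followed as written, 4.7 pools the two randomized arms in the RW adverse-event tables, at odds with the objective in 1.3 and with the other safety summaries in the same section. It should be fixed.

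Confidence is medium, because 3.2 allows the other reading and because versions 1.0 and 2.0, used for the earlier open-label and RW analyses, are not available. An arm-level RW table may already exist, and the text does not show that any table was in fact pooled.

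The size is a loss of information, not a bias that can be estimated: a pooled cell is compatible with arm differences up to twice the pooled percentage in either direction. That rests on equal arms of at most 78 and, in the worked examples, on assumed event counts.

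**What to change.** In SAP 4.7, state that TEAEs in the RW phase (by SOC and preferred term, by maximum severity, and by relationship) are presented in separate simufilam and placebo columns, as treated, with the number of patients in each arm as denominator. State that the comparison is descriptive.

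If an annualized rate is reported for RW, define its period at risk by arm, from first randomized dose to Month 18 or early termination.

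As a wording clarification only, say that events in patients kept on open-label drug after Month 12 and before Withdrawal Day 1 count as open-label.

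The cost is a few sentences in the SAP and a column split in tables already planned. No new data are needed.
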